3.3 Exposure definition and measurement

To identify users of oral glucose lowering medications, including rosiglitazone, we will use the Aarhus University Prescription Database (AUPD)¹⁶ in Denmark and the General Practice Research Database (GPRD) in the UK.¹⁷ The AUPD tracks prescription dispensations, while the GPRD records prescriptions issued by physicians. Antidiabetic medications are available by prescription only in both countries.

We will identify patients with *two or more* prescriptions for oral glucose lowering drugs redeemed (in Denmark) or issued (in UK) between 1 January 2000 and 1 January 2011. Because dispensed prescriptions contain personal identifiers, we will be able to determine the number of unique users of each oral glucose lowering drug or their combinations. Currently, AUPD contains data on approximately 2,400, while GPRD has data on approximately 20,000 users of rosiglitazone preparations.

Based on recorded prescription dates, we will examine the patterns of oral glucose lowering drug use during the study period. A person will be considered a switcher once they have received two or more prescriptions for a new therapy. Users will be classified into several categories (not all drug combinations listed below may exist in the actual data):

- Those who receive rosiglitazone monotherapy as the first oral glucose lowering drug;

- Those who use oral glucose lowering drugs other than rosiglitazone (classified by type of drug);
- Those who switch from oral glucose lowering drugs other than rosiglitazone to rosiglitazone;
- Those who switch from rosiglitazone to an alternative oral glucose lowering drug. This group may include people who received alternative oral glucose lowering drugs before rosiglitazone use;
- Those in whom rosiglitazone is added to a prior alternative therapy;
- Those in whom an alternative oral glucose lowering drugs is added to rosiglitazone therapy.

List of medications, with codes used to identify them, appears in Appendix 1.

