3.6 Analysis plan

3.6.1 Drug utilization patterns

Based on the dates of rosiglitazone marketing, publications, and regulatory decisions, the following four broad periods can be identified, in which drug utilization patterns will be examined, starting with 1 July 2000, when rosiglitazone was introduced to the EU market:

- | | |
|----------|---|
| Period 1 | 1 July 2000 to 23 May 2007 (meta-analysis & by EMA's press release) |
| Period 2 | 24 May 2007 to 24 January 2008 (EMA adds contra-indications) |
| Period 3 | 25 January 2008 to 22 September 2010 (EMA suspends rosiglitazone) |
| Period 4 | 23 September 2010 until data closing date. |

We will evaluate prescribing patterns within these periods and according to calendar month by several methods. First, we will calculate (separately in Denmark and in the UK):

- The number of persons receiving prescriptions for rosiglitazone in each time period, overall and per month during the time period;
- The number of prescriptions for rosiglitazone in each time period, overall and per month during the time period;
- The number of persons receiving a prescription for any specific antidiabetic medication in each time period, overall and per month during the time period;

- The proportion of persons receiving a prescription for any specific antidiabetic medication who received a prescription for rosiglitazone in each time period.

We will describe switching patterns in several ways within each database. First we will determine the proportion of patients on anti-diabetic therapies other than rosiglitazone who switched to rosiglitazone in each of the 4 time periods. We will also describe the proportion of people, by time period, who switched from rosiglitazone to another anti-diabetic medication or who discontinued use of any anti-diabetic medication. Proportions of patients discontinuing rosiglitazone preparations will be determined among those who originally switched to rosiglitazone and among those for whom the rosiglitazone-containing product was the first-ever anti-diabetic prescription. Switching will be defined as 1) stopping all rosiglitazone prescriptions and starting a different anti-diabetic medication, 2) stopping all anti-diabetic medications or 3) adding new anti-diabetic therapies to the current rosiglitazone therapy (concomitant therapies). A person will be considered a switcher once they have received at least 2 prescriptions for a new therapy.

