3.6.3 Acute drug reactions

For patient-level endpoints, baseline will be defined as the recorded date of medication switch/addition (as reflected by a new dispensation/issue); date of the first-time prescription dispensation/issue (in first-time users) or 1 January 2000 (in prevalent users).

We will examine the number of potential drug reactions occurring within 45 days of baseline and calculate the 45-day cumulative incidence of acute drug reactions, overall and diagnosis-specific (if the data set is large enough); We will estimate risk ratios for the acute drug reactions identified using regression, while adjusting for confounding.

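### A patient who stops only rosiglitazone and stays on a separately prescribed antidiabetic drug fits none of the protocol's switching definitions and has no baseline for follow-up after leaving rosiglitazone

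*Protocol*

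**What the plan says.** Protocol section 3.6.1 defines switching by three routes: "1) stopping all rosiglitazone prescriptions and starting a different anti-diabetic medication, 2) stopping all anti-diabetic medications or 3) adding new anti-diabetic therapies" to the rosiglitazone already in use. It then sets an operational rule: "A person will be considered a switcher once they have received at least 2 prescriptions for a new therapy". Section 3.3 has the same rule.

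Section 3.6.1 also reports the proportion discontinuing rosiglitazone, in two groups: "among those who originally switched to rosiglitazone and among those for whom the rosiglitazone-containing product was the first-ever anti-diabetic prescription".

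Section 3.3 sorts users into categories. One is "Those who switch from oral glucose lowering drugs other than rosiglitazone to rosiglitazone". A separate one is "Those in whom rosiglitazone is added to a prior alternative therapy". On the category that switches away from rosiglitazone, it adds: "This group may include people who received alternative oral glucose lowering drugs before rosiglitazone use".

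For patient-level endpoints, section 3.6.3 says "baseline will be defined as the recorded date of medication switch/addition (as reflected by a new dispensation/issue"). The alternatives are the first prescription in first-time users and 1 January 2000 in prevalent users. The laboratory comparisons in section 3.6.4 are made before and after that baseline.

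**The concern.** The protocol expects combination use: it has an add-on category, and Appendix 1 codes two fixed combinations containing rosiglitazone. One plain response to a warning or to the suspension is then to drop rosiglitazone and carry on with the other drug. The definitions have no place for that response.

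Aims 4 and 5 ask about acute reactions and glycaemic control in patients moving to or from rosiglitazone, and the commission asks about the condition of its users. If only patients who receive a replacement can be followed after leaving, the results describe a selected group of leavers. Definition causes that selection, not missing data.

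**Working it through.** No figure in the protocol bears on this, so the check is to apply the rules to every possible change.

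**Step 1: the three routes.** Let R be rosiglitazone and M and S two other drugs, each prescribed separately. Read starting or adding as taking a drug not in the previous regimen. List every change after which R is no longer taken.

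| Withdrawn from | Possible changes | Route 1 (replace) | Route 2 (stop all) | No route |
|---|---|---|---|---|
| R alone | 4 | 3 | 1 | 0 |
| M+R | 4 | 2 | 1 | 1 |
| R+S | 4 | 2 | 1 | 1 |
| M+R+S | 4 | 0 | 1 | 3 |
| Total | 16 | 7 | 4 | 5 |

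Route 3 does not arise because R continues there. From combinations alone there are 16 − 4 = 12 changes: 4 by route 1, 3 by route 2 and 5 by none. The five are M+R to M, R+S to S, and M+R+S to M, to S or to M+S. They are exactly the changes in which the patient stays on existing drugs. They count kinds of change, not patients.

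**Step 2: the two-prescription rule.** Only the 7 route 1 changes bring in a new drug. The other 16 − 7 = 9 cannot yield two prescriptions for a new therapy: the 5 above and all 4 route 2 changes. Section 3.6.1 therefore counts stopping everything as switching in one sentence and makes it unattainable in the next.

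**Step 3: baseline.** With no new dispensation, section 3.6.3 sets no date at withdrawal. Such a patient may have a baseline from when rosiglitazone was started or added, so entry can be analysed. Leaving cannot.

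**Step 4: packaging.** A patient moving from the fixed rosiglitazone and metformin product to plain metformin receives a product not dispensed before, which could count as starting a different medication under route 1. The same ingredient change made from separate tablets cannot.

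**Step 5: discontinuation denominators.** Section 3.3 lists switching to rosiglitazone and having it added as different categories. On that classification add-on users are in neither denominator. Section 3.6.1 leaves switching to rosiglitazone undefined, counts an addition as switching (though only for additions to rosiglitazone), and its two-prescription rule would admit an add-on user. On that reading nobody is lost. The add-on share is not stated. For an assumed share of 10% to 90%, section 3.3's reading leaves out:

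- Denmark: 2,400 × 0.10 = 240 to 2,400 × 0.90 = 2,160
- UK: 20,000 × 0.10 = 2,000 to 20,000 × 0.90 = 18,000

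On the other reading the number is 0 in both countries.

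**The case against.** A reader might infer that withdrawal from combination therapy goes largely unmeasured and that the response to each milestone is understated. The protocol does not support that. Section 3.6.1 counts "The number of persons receiving prescriptions for rosiglitazone in each time period, overall and per month during the time period", and prescriptions likewise, whatever the regimen, and the sliding-window plots set these against the milestone dates. A patient who drops rosiglitazone and keeps metformin lowers those curves like any other leaver. The discontinuation proportion is not tied to the three routes, so it too counts this withdrawal within its two groups. What stands is that neither measure shows the exit route or links the patient to an outcome.

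A reader might also infer that add-on users are certainly excluded from the discontinuation denominators. Step 5 shows that this holds on one reading only; the defect is an unresolved conflict between two sections.

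Nor do the documents support a direction of bias. Patients withdrawn without replacement may lose control, or may have been chosen because control was already good.

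Finally, it can be said that withdrawal without replacement lies at the edge of aims 4 and 5, which speak of switching between rosiglitazone and alternatives. But section 3.6.1 itself counts stopping all treatment as switching, so exits without replacement are in scope on the protocol's own terms. The note in section 3.3 on drugs received before rosiglitazone does not settle the matter, because it is silent on a drug taken alongside and continued.

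**Conclusion.** The gap is real on the plain text. A patient who stops separately prescribed rosiglitazone and continues existing treatment meets no switching route, cannot satisfy the two-prescription rule and has no withdrawal baseline. This exit is missing from the switching proportions and from the acute-reaction and laboratory analyses of leaving rosiglitazone. It is not missing from the measured fall in use. Two related faults come with it: classification can depend on product packaging, and patients who stop everything fail the switcher rule.

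The size in patients is unknown. The count of 5 in 12 rests on two companion drugs, separate prescribing and the reading of starting as taking a drug not already in the regimen. The protocol gives neither the share on combination therapy nor the share who leave without a replacement.

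**What to change.** - **Section 3.6.1:** add a fourth route, defined by ingredient: rosiglitazone withdrawn, other antidiabetic therapy continued, no new drug. Exempt this route and the stop-everything route from the rule of two new prescriptions.
- **Section 3.6.3:** set the baseline for the new route at the estimated end of the last rosiglitazone supply. The next refill of the other drug should not be used: a patient must survive to collect it, so deaths and events before it would be lost, and all-cause mortality within 45 days is an endpoint. For the same reason, judge continuation by supply of the other drug in hand at that date. Vary the assumed supply length and grace period in a sensitivity analysis, and report the route as its own group in the 45-day and laboratory analyses.
- **Sections 3.3 and 3.6.1:** state that add-on users are included in the discontinuation denominators, and report discontinuation by mode of entry.

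The cost is protocol wording and one exposure category built from prescription data already held. The withdrawal date will be inferred. For the UK, section 6.2 lists quantity and dosing instructions. For Denmark, section 6.1 lists drug code, date and product number but no days' supply.

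Follow-up after the suspension is also short. From 23 September 2010 to the end of the study window on 1 January 2011 is 100 days. If follow-up stops there, a full 45 days requires supply to have ended within 100 − 45 = 55 days of the suspension. Stated Danish laboratory coverage ends in 2008 (North) and September 2009 (Central). Unless it is extended, Danish patients withdrawn after the suspension will have no laboratory follow-up under any definition.

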In the UK, the study will be conducted based on data from the General Practice Research Database (GPRD). The GPRD is an ongoing longitudinal database that collects data from over 350 general practices in the UK since 1987. The UK provides a unique medical environment to create a computerized medical data resource for medical epidemiological research for two main reasons: a) the primary health care system comprehensively covers the UK population; b) the information on all relevant medical care is located in the offices of the general practitioners (GPs), who function as "gatekeepers" for hospital and specialist referrals in the UK health system. The GPRD contains information on more than 6 million patients, of whom 3.5 million are currently registered, and a

cumulative follow-up time of more than 40 million person-years. It covers 6% of the UK population; this sample is representative with respect to age, gender and race/ethnicity distribution.

The study population will include, in both countries, diabetic patients treated with oral glucose lowering drugs between 1 January 2000 and 1 January 2011. This period covers the time from the approval of rosiglitazone for use in the European Union, in July 2000, until the decision by the European Medicines Agency to suspend the drug, on 23 September 2010. The study period also includes a pre-approval and a post-suspension periods to allow examination of drug utilization patterns in response to these events.

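### The two-prescription switching rule has no run-out after the suspension period, so the Period 4 switching proportion is biased downward relative to Periods 1-3.

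*Protocol*

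**What the plan says.** The rule appears twice in the protocol. Section 3.3 has "A person will be considered a switcher once they have received two or more prescriptions for a new therapy", and section 3.6.1 repeats it as "A person will be considered a switcher once they have received at least 2 prescriptions for a new therapy".

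The end of the data is described in two ways:

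- Section 3.1 defines the population as "diabetic patients treated with oral glucose lowering drugs between 1 January 2000 and 1 January 2011" and gives the suspension as "the decision by the European Medicines Agency to suspend the drug, on 23 September 2010". Section 3.3 identifies patients from prescriptions "redeemed (in Denmark) or issued (in UK) between 1 January 2000 and 1 January 2011".
- Section 3.6.1 defines Period 3 as "25 January 2008 to 22 September 2010 (EMA suspends rosiglitazone)" and Period 4 as "23 September 2010 until data closing date", with no calendar date for the close.

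The quantities that use the rule are period-specific proportions. Section 3.6.1 plans the proportion of patients on other therapies who move to rosiglitazone in each period, and "the proportion of people, by time period, who switched from rosiglitazone to another anti-diabetic medication". It counts replacement, add-on and cessation of all antidiabetic treatment as forms of switching. The protocol provides no run-out after Period 4, no minimum time to confirm a switch, and no mention of truncation.

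**The concern.** A switch that needs a second prescription can be seen only if enough observed time follows the first. Periods 1-3 have that time, but in Period 4 it shrinks to nothing as data close approaches. A patient who left rosiglitazone after the suspension and had received one supply of a new drug by data close is not counted as a switcher, although the move has taken place.

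Section 3.1 says the post-suspension period is included so that utilisation in response to the suspension can be examined. A low switching proportion in Period 4 could be read as patients not being moved to alternatives, when it partly reflects how little time was left to observe the second prescription.

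**Working it through.** The protocol gives no switching figure to reproduce. The check is calendar arithmetic followed by a truncation calculation.

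**Inputs from the protocol.** Period boundaries (3.6.1), study end 1 January 2011 (3.1 and 3.3), two prescriptions needed (3.3 and 3.6.1), report dates 1 April and 1 October 2011 (section 4).

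**Assumed inputs.** The gap *g* between first and second prescription of the new drug is taken as 28, 60 or 90 days. Switching speed is either evenly spread over Period 4, or exponential from the suspension date with mean *m* of 14, 30 or 60 days. The switch is dated at the first prescription.

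**Step 1: time left to confirm a switch, with data ending 1 January 2011.**

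| Period | Length (days) | Time left for a switch on the last day (days) |
|---|---|---|
| 1 | 2518 | 1319 |
| 2 | 246 | 1073 |
| 3 | 972 | 101 |
| 4 | 100 | essentially none |

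For any gap up to 100 days, Periods 1-3 lose nothing.

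**Step 2: loss in Period 4.** With *W* = days from 23 September 2010 to data close, a first prescription after day *W* − *g* cannot be confirmed.

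- Even spread: loss = *g* / *W*. For *g* = 28 and *W* = 100 this is 28/100 = 28%.
- Front-loaded: loss = 1 − F(*W* − *g*), with F(*t*) = (1 − e^(−*t*/*m*)) / (1 − e^(−*W*/*m*)). For *g* = 28, *m* = 30, *W* = 100: F(72) = (1 − e^(−2.4)) / (1 − e^(−3.33)) = 0.909/0.964 = 0.943, so the loss is 5.7%.

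Loss of Period 4 switches with a 1 January 2011 close (*W* = 100):

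| Gap | Even spread | Mean 60 d | Mean 30 d | Mean 14 d |
|---|---|---|---|---|
| 28 d | 28% | 13.8% | 5.7% | 0.5% |
| 60 d | 60% | 40.0% | 23.6% | 5.7% |
| 90 d | 90% | 81.1% | 70.6% | 48.9% |

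**Step 3: a later close.** Report dates are upper bounds, since data must precede the report. Losses for gaps of 28 / 60 / 90 days:

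| Close | *W* | Even spread | Mean 60 d | Mean 30 d |
|---|---|---|---|---|
| 1 April 2011 | 190 | 14.7 / 31.6 / 47.4% | 2.6 / 7.6 / 15.3% | 0.3 / 1.1 / 3.4% |
| 1 October 2011 | 373 | 7.5 / 16.1 / 24.1% | 0.1 / 0.3 / 0.7% | 0.0 / 0.0 / 0.0% |

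Moving the close and the end of Period 4 together reduces the loss but does not remove it by design, because the last refill interval before close always stays unconfirmed.

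**Step 4: which measures are touched.** The rule affects replacement and add-on switches. Cessation of all treatment involves no new therapy, so the rule cannot apply to it as written. The counts of persons and prescriptions, the proportion receiving rosiglitazone, and the sliding-window plots built on these four parameters need no second prescription.

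**The case against.** The strongest reply is that the close is not settled. Section 3.6.1 leaves it undated, section 4 lets the final report add data that arrive later, and the date range in section 3.3 sits in a sentence about identifying patients. With a later close and prompt switching after a suspension, the loss could be trivial. This stands as a limit on size: the 100 days follow from sections 3.1 and 3.3, but the document does not commit to them throughout. It does not remove the defect, because the plan provides no run-out under any close. Nor is prompt switching assured. The protocol's background dates the European Commission's suspension decision to 3 December 2010, which leaves 29 days to 1 January 2011. A switch begun after it with a refill gap of 30 days or more could not be confirmed by then.

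It is also fair that two prescriptions guard against trial fills, and that follow-up details often belong in a SAP. The guard is worth keeping. But the protocol itself fixes both the rule and the window, and together they make the periods non-comparable.

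Three stronger readings are tempting and are not supported:

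- *The Denmark-UK comparison is biased.* The possible model in section 3.6.1 compares prescription numbers or proportions receiving prescriptions, not switcher status. Switching is described within each database, and no between-country contrast of it is specified.
- *Uptake of rosiglitazone would seem to fall before each milestone.* That needs a time series of switches. The plan reports switching only by broad period, and its plotted parameters count single prescriptions. One 28- to 90-day interval is 1.1% to 3.6% of Period 1 (28/2518 to 90/2518).
- *The response to the suspension cannot be measured.* Rosiglitazone counts and discontinuation of rosiglitazone are reported without the rule, so departure from the drug is still seen.

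**Conclusion.** The point holds for the proportion of replacement and add-on switches in Period 4, which is biased downward relative to Periods 1-3. With data ending on 1 January 2011, the loss is between 0.5% (28-day gap, mean time to switch 14 days) and 90% (90-day gap, even spread). A later close makes it smaller, and negligible if patients switched quickly. The direction follows from the plan; the size rests on refill gaps and switching speed that the protocol does not give.

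One further assumption is that a switch is dated at its first prescription. Section 3.6.3 points that way for patient-level endpoints, but section 3.6.1 does not say. If the second prescription sets the date, some switches begun late in Period 3 move into Period 4 and partly offset its total, while those begun late in Period 4 are still missed.

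**What to change.** 1. Reconcile the end dates in sections 3.1, 3.3 and 3.6.1, and give the data closing date as a calendar date.
2. Keep the two-prescription rule, date the switch at the first prescription, and accept confirming prescriptions up to the actual data closing date.
3. Apply one fixed confirmation time to switches in every period, for example 120 days, and end Period 4 switch dates that far before data close. Gaps longer than this are then missed equally in all periods.
4. If Period 4 becomes too short, report a one-prescription version for all periods as a sensitivity analysis.

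The confirmation time has to be chosen with the close in view. A 120-day rule leaves 190 − 120 = 70 days of Period 4 switch dates with a 1 April 2011 close and 373 − 120 = 253 days with a 1 October 2011 close. With a 1 January 2011 close it leaves none (100 < 120) and also cuts into the end of Period 3, which has only 101 days of run-out. A 60-day rule would then leave 100 − 60 = 40 days.

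The cost is protocol wording and one more programming run, using data already held apart from any later prescriptions needed for confirmation. The downside is a shorter accrual window in Period 4, or some trial fills in the sensitivity version.
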